## 1.6 POTENTIAL BENEFITS

The findings of this study will contribute to guide doctors and patients in the treatment of sciatica. Despite little evidence for being effective NSAIDs are currently regarded as standard therapy for sciatica and are in widespread use in clinical practice. If the results of the present study turn out negative, i.e. the effect is not better than placebo or not considered clinically relevant, future patients can be spared from an ineffective and potentially harmful treatment. Conversely, if Naproxen is shown to be effective, the results of this study will enable the medical community and patients to judge whether the positive effects outweigh the adverse events.

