### **7.1.2 Non-serious AEs**

Since the AE profile of Naproxen is well established, non-serious AEs will be recorded, but not reported to the Norwegian Medicines Agency. The same goes for Paracetamol. The eCRF will include a daily checklist including expected non-serious AEs (see section 7.2) as well as space to specify other unpleasant events.

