## **7.3 TIME PERIOD FOR REPORTING AE AND SAE**

In this study, participation implies daily recording of patient reported outcomes. Concurrently patients will be asked to report any potential AEs on a daily basis. Additionally, at the follow up at 5 ( $\pm 1$ ) and at the final study visit we will inquire about AEs. During the course of the study all SAEs will be proactively followed up for each patient; events will be followed up to resolution, unless the event is considered by the investigator to be unlikely to resolve due to the underlying disease. Every effort will be made to obtain a resolution for all SAEs, even if the events continue after discontinuation/study completion.

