## **7.4 RECORDING OF ADVERSE EVENTS**

### **7.4.1 Non-serious AEs**

Patients may record non-serious AEs on a tick off list including 10 events expected for Naproxen, see section 7.2.1. Additionally, patients may report other non-serious AEs in their own words. At the follow-up at 5 ( $\pm 1$ ) at the final study visit the investigator will record whether the event is resolved or still ongoing and whether any action was taken.

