29.2 Post hoc analyses

Any post-hoc exploratory analyses not identified in this SAP will be clearly identified as unplanned analyses. If unexpected missing data patterns are found in the data, we may conduct sensitivity analyses in addition to those predefined in this SAP.

30 Safety

An adverse event is an untoward medical occurrence after the administration of the first dose of a study drug through day 12 (± 2). The number of non-serious and serious adverse events, and the proportion of subjects reporting ≥ 1 adverse event, will be summarized by treatment group and severity (mild / moderate / severe). We will also report the number and reasons for treatment discontinuation because of a treatment-related adverse event, as judged by the principal investigator. AEs will be summarized by frequencies and percentages and analyzed with chi-square tests.

31 Statistical software

Data manipulation, tables, figures, listings and analyses will be performed and documented using R, Stata and IBM-SPSS software.

32 Statistical summaries

For tables, sample sizes for each treatment group will be presented as totals in the column header (N=xxx), where appropriate. Sample sizes shown with summary statistics are the number (n) of patients with non-missing values. Summaries for categorical variables will include only categories that patients had a response in. Percentages corresponding to null categories (cells) will be suppressed. Summaries for continuous variables will include mean and SD. Other summaries (e.g. median, quartiles or range) will be used as appropriate. Percentages will be rounded and reported to a single decimal place. Summaries that include p-values will report the p-value to three decimal places with a leading zero (0.001). P-values <0.001 will be reported as <0.001.

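### SAP 30 plans chi-square tests for adverse events but no between-group risk difference with a confidence interval, and leaves the tested unit unstated

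*SAP*

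**What the plan says.** SAP 30 (Safety) names two quantities. The first is a count: "The number of non-serious and serious adverse events". The second is at patient level: "the proportion of subjects reporting ≥ 1 adverse event, will be summarized by treatment group and severity". It then adds: "AEs will be summarized by frequencies and percentages and analyzed with chi-square tests". It does not say which quantity is tested. Planned Table 7 (SAP 32.1) is described only as AEs by group and severity.

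The data come largely from a diary. Protocol 7.1.2 says: "The eCRF will include a daily checklist including expected non-serious AEs". Protocol 7.4.1 adds: "Patients may record non-serious AEs on a tick off list including 10 events expected for Naproxen". Treatment lasts 10 days. The flow chart in protocol 6.1 also has investigators asking about AEs at day 5, at the final visit and at withdrawal.

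On the benefit side, planned Table 2 has a column for the between-group difference with its 95% interval, and it covers percentage outcomes too. SAP 27.2 gives responders a number needed to treat with an interval. SAP 18 promises 95% intervals for parameter estimates in general.

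Protocol 1.6 states what the results are for: if naproxen proves effective, the medical community and patients will be able "to judge whether the positive effects outweigh the adverse events".

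**The concern.** Weighing benefit against harm needs both on a comparable scale, with their uncertainty. The plan supplies this for benefit. For harm it supplies arm percentages and a test. A chi-square test estimates no parameter, so the general rule in SAP 18 has nothing in SAP 30 to attach to. In a trial sized for a pain score, most AE tests will be non-significant whether or not there is an excess, and a table of such p-values is easily read as showing no harm.

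The second gap is the unit. A symptom that persists can be ticked on up to 10 days, and the same event may also reach the investigator's record. No rule merges these entries into one event. Records from one patient are correlated, and a chi-square test assumes independent units. If an analyst tested records rather than patients, differences could be declared that are not there.

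**Working it through.** **Inputs from the documents.** Sample size: difference 1.5, SD 2.5, two-sided 5%, 90% power, 20% allowance, 60 per arm and 150 in total, allocated 1:1 (protocol 4.6 and 9.1, SAP 11). Tick list: 10 items, daily for 10 days. Dyspepsia on naproxen: 14% (protocol 1.5.3).

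**Assumptions.** The documents give no placebo AE rate and no within-patient correlation of daily ticks. Placebo rates of 5%, 7% and 10% and correlations of 0 to 0.7 are used below to show the range.

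**1. The plan's own figure.** n = 2(1.96 + 1.2816)² × 2.5²/1.5² = 58.4, so 59 per arm. The t-test version gives 59.4, so 60. Inflated: 120/0.80 = 150, or 75 per arm. The sample size reproduces. The documents give no figure for the AE analysis.

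**2. Power of a patient-level chi-square test.** Power = Φ[(d − 1.96·SE₀)/SE₁], with SE₀ from the pooled proportion and SE₁ from the separate proportions. For 14% against 7% at 75 per arm:

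- d = 0.07 and pooled p = 0.105
- SE₀ = √(2 × 0.105 × 0.895/75) = 0.0501
- SE₁ = √[(0.14 × 0.86 + 0.07 × 0.93)/75] = 0.0497
- Power = Φ(−0.565) = 0.286 (exact binomial calculation: 0.290)

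| Naproxen vs assumed placebo | 75 per arm | 60 per arm |
|---|---|---|
| 14% vs 5% | 47% | 39% |
| 14% vs 7% | 29% | 24% |
| 14% vs 10% | 11% | 10% |

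**3. What an interval adds.** Take 10/75 against 5/75.

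- Chi-square: pooled p = 15/150 = 0.10, variance = 0.10 × 0.90 × 2/75 = 0.0024, χ² = 0.0667²/0.0024 = 1.85, p = 0.17.
- Risk difference: 13.3% − 6.7% = +6.7 points. The Newcombe 95% interval is −3.3 to +16.9.

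The test result alone reads as no difference. The interval shows that an excess of up to about 17 points is not excluded.

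**4. Sparse cells.** An expected count of 5 per arm needs 10 of 150 patients (6.7%) with the event. At 2 patients against 0, chi-square gives p = 0.155 and Fisher's test 0.497. At 0 against 0, the Newcombe interval is still informative: −4.9 to +4.9 points.

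**5. If daily ticks were tested as independent records.** With 10 records per patient and within-patient correlation ρ, the design effect is 1 + 9ρ, and type I error ≈ 2[1 − Φ(1.96/√(1 + 9ρ))]. This was checked by beta-binomial simulation: no true difference, 75 per arm, daily tick rates of 5% and 14%, 20,000 runs per scenario.

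| ρ (assumed) | Design effect | Formula | Simulated |
|---|---|---|---|
| 0 | 1.0 | 5.0% | 4.9–5.0% |
| 0.1 | 1.9 | 15.5% | 15.4–15.7% |
| 0.3 | 3.7 | 30.8% | 31.1–31.2% |
| 0.5 | 5.5 | 40.3% | 40.2–40.5% |
| 0.7 | 7.3 | 46.8% | 47.8% |

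In the same simulations, the chi-square test on patients with at least one event rejected in 4.8% to 6.2% of trials.

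**The case against.** A reader might infer that SAP 30 plans to test recorded events, so that its AE tests are invalid. The documents do not support this. The proportion of patients with at least one AE is named in the same section. A percentage needs a denominator, and the only ones in SAP 32 are patients. A raw event count has no complement to fill a 2×2 table, and patient-days appear in neither document. SAP 30 defines an AE as an occurrence, not a tick, and protocol 7.4.1 has the investigator record whether an event has resolved or continues. The natural reading is patients with an AE out of patients in the arm, and that test is sound. The inflated error rates in step 5 therefore describe a possible misreading, not the stated plan.

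A reader might also infer that harms will be reported by p-value alone. That is too strong as well. Percentages by arm are planned, and with the arm sizes shown anyone can compute a risk difference and its interval. AEs are neither a primary nor a secondary endpoint, and no decision rule depends on these tests.

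The inputs are soft too. The 14% comes from double-blind and open-label trials together, with no placebo rate and no stated link to 10 days of use. The low power reflects the sample size and would not improve under a different summary.

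All of this stands. It makes the clustering problem conditional and limits the seriousness of the point. It does not supply the missing effect measure, the tested unit or the rule for merging ticks.

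**Conclusion.** The point holds as a low-cost improvement, not as an error that invalidates the safety analysis. The firm part does not depend on how SAP 30 is read: harms get arm percentages and a test, efficacy gets differences with 95% intervals, and protocol 1.6 expects the two to be weighed together. A non-significant AE test at this sample size carries little information. Power for a 14% rate is between about 10% and 47% over assumed placebo rates of 5% to 10% and 60 to 75 patients per arm.

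The conditional part is a gap in specification. The tested unit and the merging of daily ticks are not stated. If records were tested as independent, type I error would be about 15% to 48% for assumed correlations of 0.1 to 0.7, and 5% at zero. With the patient as unit it stays near 5%.

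**What to change.** In SAP 30 and planned Table 7:

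- Count each patient once per AE term, whatever the number of days ticked and whether the source is the diary or the investigator.
- For each arm of the safety population, report the number and percentage of patients with any AE, with each listed term and with any serious AE.
- Give the risk difference with a 95% interval, for example Newcombe's, in place of chi-square p-values. This also copes with sparse and empty cells.
- Show numbers of events descriptively, without a test.

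Data collection does not change. The cost is a few lines of SAP text and a simple recode of the tick list. The downside is that there is no p-value for AEs. The change should be made before the treatment codes are revealed, so that the unit and the summary are not chosen with the results in view.

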32.1 Planned tables

- Table 1. Baseline characteristics of participants by treatment group
- Table 2. Intervention effect on primary and secondary outcomes
- Table 3. Important and not important protocol deviations by treatment group
- Table 4. Baseline concomitant medications by treatment group
- Table 5. Response to blinding question at day 10
- Table 6. Global perceived change (including all response categories) at day 5 and day 10 by treatment group
- Table 7. Adverse events by treatment group and severity (mild / moderate / severe)
- Table 8. Results of sensitivity analyses

32.2 Planned listings

- List 1. Inclusion and exclusion criteria
- List 2. Measurements and timing
- List 3. Reasons for non-adherence to the intervention
- List 4. Reasons for withdrawing participants from the study

32.3 Planned figures

- Figure 1: CONSORT Diagram
- Figure 2: Outcome scores over the 10-day treatment period, by treatment group. (Panel A; leg pain intensity, panel B; back pain intensity, panel C; disability)
- Figure 3: Self-reported use of study medication over time, by treatment group
- Figure 4: Proportions of subjects adherent to the intervention over time, by treatment group
- Figure 5: Proportions of subjects compliant to follow-up over time, by treatment group

33 References

33.1 Data Handling Plan

The data handling plan was developed by the Clinical Trial Unit, Oslo University Hospital, and approved 27 oct 2017.

33.2 Statistical Master File

After database lock the clinical datasets will be delivered to the sponsor specified as SPSS files, one file per form as specified in the data handling plan. The data will be analyzed blinded to the randomization codes. Each participant will be provided with a code A or B. When the analyses of the data are complete the investigators will be provided with which treatment (Naproxen or placebo) code A and B represents.

33.3 Procedures or documents to be adhered to

This SAP was developed based on Gamble et al; Guidelines for the Content of Statistical Analysis Plans in Clinical Trials [6]

The following documents were reviewed:

- Clinical Research Protocol for NSAIDs in sciatica (NIS) version no. 2.3
- e-CRF for NIS, Viedoc 4.37, 2017-11-01
- ICH Harmonized Tripartite Guideline on Statistical Principles for Clinical Trials [7]
- ICH Harmonized Tripartite Guideline on Estimands and Sensitivity Analysis in Clinical Trials [8]
- ICH Harmonized Tripartite Guideline on Structure and Content of Clinical Study Reports [9]
- EMA Guideline on Missing Data in Confirmatory Clinical Trials [10]

Ever taken/used NSAIDs, n (%)		
Number of previous sciatica episodes, median (IQR) or mean (SD)		
Duration of current sciatica episode (weeks), median (IQR) or mean (SD)		
Previous back surgery, n (%)		
Treatment received for back problems (last month), n (%)		
Physiotherapy/chiropractic		
Other?		
Imaging findings*, n (%)		
Disc herniation		
Other†		
Imaging not performed		
Clinical examination findings, n (%)		
Sensory deficit,		
Motor deficit‡, n (%)		
Reflex deficit§, n (%)		
Pain on straight-leg raising maneuver, n (%)		
Leg pain intensity score (0-10), mean (SD)		
Back pain intensity score (0-10), mean (SD)		
Roland Morris Disability Questionnaire for Sciatica score (0-23), mean (SD)		
Sciatica Bothersomeness Index score (0-24), mean (SD)		
Concomitant use of pain medication, no (%)		
Any pain medication		
Weak opioids		
Strong opioids		

* Lumbar MRI or computed tomography (CT)

† No findings (n=), spondylosis (n=), etc.

‡ Reduced unilateral leg stand (Trendelenburg test), or toe or heel walking, or knee extension, or ankle flexion or extension, or big toe extension

§ Achilles or patellar

Planned Table 2. Intervention effects

	Naproxen (N=)	Placebo (N=)	
	Mean* or percentage (95% CI)	Mean* or percentage (95% CI)	Difference (95% CI)
Primary outcome			
Change in leg pain intensity			
Secondary outcomes			
Change in back pain intensity			
Change in disability			
Change in sciatica bothersomeness			
Percentage of participants with $\geq 30\%$ improvement in leg pain intensity			
Percentage of participants with $\geq 50\%$ improvement in leg pain intensity			
Likert score for global perception of change			
Percentage of participants unable to work or study full time due to back problems			
Rescue medication consumption †			
Concomitant use of weak opioids ‡			
Concomitant use of strong opioids §			

* Least square means

† Paracetamol tablets

‡ Quantified by defined daily dose (DDD)

§ Quantified by morphine milligram equivalents (MME)
